## 5.4. Experimental Visit

### 5.4.1. Randomization

Participants who are eligible after the physical exam will be randomized to an experimental condition (i.e., endotoxin vs. placebo) within an appropriate amount of time based on study physician discretion. Urn randomization will be used to balance the two groups by gender and BDI-II severity. The UCLA Research Pharmacy will manage the blind. The two treatment conditions will not be different in appearance or method of administration. However, it is

possible that participants undergoing the endotoxin challenge who feel very symptomatic may suspect that they are in the active condition. For this reason, we have decided to exclude individuals who experience severe sickness symptoms as described below (which is expected to be less than 5% of the sample). If participants are withdrawn from the study due to sickness symptoms, their data will be retained for the purposes of reporting adverse events and safety data during the trial. Additional subjects will be recruited to replace the withdrawn individuals.

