#### **6.2.31. Physical Sickness Symptoms Assessment**

Symptoms of physical sickness will be self-reported during each experimental visit on a scale from 0 (symptom not present) to 4 (very severe) at multiple time points (baseline, T1, T2, T3 and T4). At the baseline assessment, participants must have a total score below 10 in order to move forward with the experimental challenge. Scores of 10 or above will result in the visit being rescheduled when the participant is feeling better. Participants who rate any symptom as a '4' at the T1 – T4 assessment will be withdrawn from the study prior to the cue-reactivity paradigm. Research staff will contact the study physician and/or nurse practitioner on call to manage any severe sickness symptoms reported during the experimental session.

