#### **6.2.42. Timeline Follow Back (TLFB)**

The Time Line Follow Back will be administered to assess quantity and frequency of alcohol, cigarette and marijuana use and will be completed at the initial screening (for the 30 days prior to that visit) and at each subsequent visit to gather data for every day prior to and including the last visit. Information obtained in this interview will be recorded on the TLFB Calendar and transcribed to the database.

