### **8.1. Statistical Power**

A power analysis was conducted for the study based on results from a previous human endotoxin challenge carried out in a control sample by our collaborators ([name] et al., 2010). Effect size was calculated based on [name] et al.'s reported sample size of  $N = 39$  and  $F$ -statistic of 8.13 for increase in negative mood at T2 after endotoxin infusion, yielding Cohen's  $d = 0.4687$ . Power analysis was conducted according to Cohen's guidelines to determine the sample size needed to achieve a power  $\geq 0.80$  (i.e. 80%) at an alpha level of .05. Using the program G\*Power version 3.1 and selecting the repeated measures ANOVA, within-between interactions design, where alpha = .05, effect size  $f = 0.234$ , we arrived at a total  $N = 76$  completers (38 heavy drinkers and 38 healthy controls). Specifically, we powered the study

to detect differences from baseline to peak (T2) inflammatory response, given that the remaining data points post-peak tend to be similar and may obscure the effects of the inflammatory challenge. Individuals who experience severe sickness symptoms will be excluded (expected to be <5% of the sample).

**8.2. Aim 1: To test that low dose endotoxin will increase cue-induced craving for alcohol in heavy drinkers as compared to light drinking controls, and as compared to placebo.**

Repeated measures analyses of variance (ANOVAs) will be conducted using PROC GLM in SAS Statistical Software. Specifically, in the repeated measures ANOVA models, Group (Heavy drinking versus light drinking) will be a two level between-subjects factor, Treatment (endotoxin vs. placebo) will be a two level between-subjects factor, and Cue (water cues versus alcohol cues) will be a between-subjects factor. The dependent measure will be self-reported alcohol craving captured by the Alcohol Craving Questionnaire. Sickness symptoms and drinking history (i.e., drinks per day and drinks per drinking day in past year) will be used as covariates in these analyses.

**8.3. Aim 2: To test whether low dose endotoxin (0.8 ng/kg of body weight) will increase depressed mood as compared to placebo.**

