Repeated measures ANOVAs in which Group (Heavy drinking versus light drinking) will be a two level between-subjects factor, and Treatment (endotoxin vs. placebo) is a two level between-subjects factor. The outcome measure is depressed mood (captured by the POMS). Sickness symptoms and drinking history will also be included as covariates in these analyses.

**8.4. Exploratory Analysis: To test associations between plasma levels of proinflammatory cytokines (IL-6 and TNF- $\alpha$ ), depressed mood, and alcohol craving during the challenge; and examine sex differences in responses to the endotoxin challenge.**

Repeated measures ANOVAs will be used to capture the effects of Treatment (endotoxin vs. placebo) by Time (T0 to T2) for the proposed planned outcomes (i.e. proinflammatory cytokines, hourly craving scores) as well as models that include sex as a between-subjects factor. As with the primary aims, sickness symptoms and drinking history will be entered in these models as covariates.

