**8.5. Exploratory Analysis: To test the effect of low dose endotoxin on neural alcohol cue-reactivity**

fMRI Data Processing: FSL 6.0 ([www.fmrib.ox.ac.uk/fsl](http://www.fmrib.ox.ac.uk/fsl)) will be used for the neuroimaging analyses. Motion correction will be carried out using the Motion Correction Linear Image Registration Tool (McFLIRT, Version 5.0) with the estimated motion parameters entered as covariates in the general linear model. Brain Extraction Tool (BET) will be used for non-brain tissue/skull removal. The images will be smoothed using a FWHM Gaussian kernel (5 mm) and high-pass filtered (100s cutoff) in the temporal domain with the FMRI Expert Analysis Tool (FEAT, Version 6.0). The EPI images will first be registered to the MBW, then to the MPRAGE using affine linear transformations, and into standard MNI space. Registration to standard space will be refined by FSL's FNIRT nonlinear registration.

**fMRI Data Analysis:** Explanatory variables for the alcohol cues task will be created by convolving delta functions representing the onset of experimental events (alcohol, non-alcohol, blurred, and fixation cues; 24-s duration) with a double-gamma hemodynamic response function in FEAT. Temporal derivatives will be included as covariates. A 2X2 ANOVA in which Group (heavy drinker versus light drinker) will be a two level between-subjects factor and Treatment (endotoxin vs. placebo) is a two level between-subjects factor. The main contrast of interest will be activation during alcohol vs. non-alcohol blocks (ALC vs. BEV). Z-statistic images will be thresholded with cluster-based corrections for multiple comparisons based on the theory of Gaussian Random Fields with a cluster-forming threshold of  $Z>3.1$  and a cluster-probability threshold of  $p<0.05$ . Sickness symptoms will also be included as covariates in these analyses.

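### Both primary models adjust for sickness symptoms without limiting the covariate to the pre-infusion score, so on the natural reading they do not estimate the endotoxin-versus-placebo effect in Aims 1 and 2

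*Combined protocol and SAP*

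**What the plan says.** Section 3.1 states both primary hypotheses as endotoxin against placebo: more cue-induced craving (Aim 1) and a larger rise in depressed mood (Aim 2). Neither is stated as an effect with sickness held constant.

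Section 8.2 (Aim 1): "Sickness symptoms and drinking history (i.e., drinks per day and drinks per drinking day in past year) will be used as covariates". Section 8.3 (Aim 2): "Sickness symptoms and drinking history will also be included as covariates in these analyses". Section 8.4 enters the same covariates, 8.5 says "Sickness symptoms will also be included as covariates in these analyses" for the imaging model, and 8.6 repeats the wording of 8.3. None names a time point for the sickness score. No section plans an analysis without it, and none defines a mediation or direct-effect analysis.

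Section 6.2.31 has sickness self-reported "at multiple time points (baseline, T1, T2, T3 and T4". At T0, "participants must have a total score below 10 in order to move forward with the experimental challenge". Section 5.4.1 accepts that it is "possible that participants undergoing the endotoxin challenge who feel very symptomatic may suspect that they are in the active condition". Sections 5.4.1, 6.2.31 and 8.1 also provide for removing participants with severe symptoms after infusion. The power calculation in 8.1 mentions no covariate.

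**The concern.** Randomisation makes the arms comparable on everything that precedes infusion. A T1 to T4 sickness score comes after infusion and is expected to differ by arm because of it. If it is a covariate, the Treatment term compares endotoxin and placebo participants who feel equally ill. Three things follow.

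- Any part of the effect on mood or craving that runs through feeling ill is taken out of the estimate.
- Sickness and Treatment are correlated, so the standard error grows even if sickness is unrelated to the outcome.
- If sickness and the outcome share other causes, such as a general tendency to report symptoms or negative affect, the adjusted comparison is biased. A treatment with no effect can appear to lower mood disturbance or craving.

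At stake is whether the two primary tests answer the questions in section 3.1. A real effect could be reported as absent, or a null effect as significant in the opposite direction.

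**Working it through.** **Which score is meant.** The analysis sections are silent. Sections 5.4.1 and 8.1 use the term for symptoms after infusion, and 8.1 does so directly before the Aim 1 model. The T0 score is capped below 10 by eligibility. Post-infusion is therefore the more natural reading, but a T0 reading is not excluded.

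**Inputs from the plan (8.1).** 76 completers, alpha 0.05, power at least 0.80, f = 0.234, baseline to T2. I assume 1:1 allocation, since no ratio is given.

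**The plan's own figure.** For a within-between interaction with k groups, m measurements and correlation rho, lambda = f² × N × m / (1 − rho). With k = 2, m = 2 and rho = 0, lambda at N = 76 is 0.234² × 76 × 2 = 8.32 and power is 0.81. The smallest N reaching 0.80 is 74, or 76 in four equal cells. So 76 is reproduced under those settings, although the plan states neither k nor rho. They correspond to a difference in change of 2 × 0.234 × √2 = 0.66 SD. I use 0.65 SD, for which unadjusted power is 0.80.

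**Assumed inputs.** The documents give neither D, the arm difference in post-infusion sickness in within-arm SDs, nor r, the within-arm correlation of sickness with the outcome contrast. I vary D over 0.5, 1 and 1.96. The last corresponds to a treatment-sickness correlation of 0.7: 2 × 0.7 / √(1 − 0.49) = 1.96.

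**Formulas.** Covariate-adjusted comparison, 38 per arm, noncentral t with 73 df:

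- adjusted effect = d − r × D
- variance inflation = 1 + D²/4
- SE = √(1 − r²) × (2/√76) × √(1 + D²/4)

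**Results at r = 0.3.** Power means rejection in the correct direction.

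| D | Variance inflation | SE | Adjusted effect, d = 0.65 | Power | Adjusted effect, d = 0 | Rejection, d = 0 |
|---|---|---|---|---|---|---|
| 0.5 | 1.06 | 0.226 | 0.65 − 0.15 = 0.50 | 0.59 | −0.15 | 10% |
| 1 | 1.25 | 0.245 | 0.65 − 0.30 = 0.35 | 0.29 | −0.30 | 23% |
| 1.96 | 1.96 | 0.306 | 0.65 − 0.588 = 0.06 | 0.04 | −0.59 | 47% |

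The d = 0 columns apply when r arises from causes that sickness and the outcome share. Nearly all of those rejections are in the negative direction.

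**Smaller r.** At r = 0.15 the adjusted effect and power are 0.58 and 0.68 (D = 0.5), 0.50 and 0.49 (D = 1), and 0.36 and 0.20 (D = 1.96). At r = 0 there is no bias, but collinearity alone lowers power to 0.774, 0.706 and 0.515.

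**Larger design effect.** If rho were 0.5, f = 0.234 would mean 0.936 SD on the change, with unadjusted power 0.98. At D = 1.5 and r = 0.3 the adjusted effect is 0.936 − 0.45 = 0.49 SD (52%), with power 0.42.

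**T0 score instead.** Randomisation makes the expected D zero, so the expected estimate is unchanged. Simulation of the Treatment-by-Group layout at a design effect of 0.662 SD gave a mean estimate of about 0.66, power of about 0.80 and type I error of 0.04 to 0.06.

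**How this maps to the planned models.** In a repeated-measures PROC GLM, a per-person covariate is also crossed with the within-person factor, so it acts on the contrast being tested. For Aim 2 I take that contrast as the T0-to-T2 change in mood. For Aim 1 it is alcohol minus water craving, because section 5.4.5 gives both cues to every participant. Here r must be the correlation of sickness with that difference, which is unknown.

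**The case against.** **The time point is not stated.** A reader might infer that the plan definitely adjusts for post-infusion sickness. The text does not say so, and if only the T0 score is meant, the bias disappears. This stands. What is on the page is a missing specification whose natural reading is harmful.

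**The severe figures depend on D.** A reader might take near-total loss of the effect, or a 47% false-positive rate, as the expected result. The documents do not support that. They give no D, expect severe sickness in under 5% of the sample, and remove participants who rate any symptom at the maximum, which trims the upper tail. The range has to be shown.

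**Aim 1 may be affected less.** Shared causes that lie at the person level raise water and alcohol ratings alike, and to that extent cancel in the difference. This also stands: the relevant r may be below 0.3. The effect of collinearity on precision remains.

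**An effect beyond feeling ill is a fair question,** especially given the unblinding worry in 5.4.1. It is, but section 3.1 does not state it as the aim, and plain covariate adjustment answers it only under assumptions that the plan does not give.

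**Drinking history.** A reader might extend the criticism to the other covariate in the same sentence. The documents do not support that. Drinking in the past year precedes randomisation, so adjusting for it does not bias the Treatment contrast. Group is defined in 5.2.1 by AUDIT score and past-month binge drinking, not by past-year quantity. Section 8.2 also does not say that the past-year measure comes from the Timeline Follow Back.

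**Conclusion.** The concern holds in this form: 8.2 and 8.3 (and 8.4 to 8.6) leave the sickness covariate open to post-infusion scores, and the protocol's own account of sickness makes that the natural reading. On that reading the primary models do not estimate the effect that Aims 1 and 2 state.

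The size cannot be settled from the documents. At r = 0.3, a 0.65 SD effect planned at about 80% power would be tested with power between 0.59 and 0.04 as D goes from 0.5 to 1.96 SD. False rejection under no effect would run from about 10% to 47%. These figures rest on assumed D and r, 1:1 allocation and a single outcome contrast. The argument is most direct for depressed mood (Aim 2). For cue-induced craving (Aim 1) the bias may be smaller. Because both primary tests are affected and the remedy is simple, this should be corrected before analysis.

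**What to change.** In 8.2 and 8.3, state that the primary model contains no sickness score taken after infusion. The T0 score may stay as a covariate if it is named as such. Any model adjusted for T1 to T4 sickness should be reported as a separate secondary direct-effect or mediation analysis, naming the time point used and the assumptions needed, in particular no unmeasured common causes of sickness and outcome. For the exploratory treatment-effect models in 8.4 to 8.6, apply the same rule or label the adjusted results in the same way.

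The cost is a change of wording only, with no new data and no change in sample size. The one drawback is that the primary estimate will include any effect that acts through feeling ill. The secondary analysis addresses that.

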#### 5.4.5. Alcohol Cue Exposure

Participants will complete an alcohol cue-exposure paradigm at baseline (T0) during the experimental visit and again approximately 2 hours after receiving intravenous endotoxin (or matched placebo). Alcohol cue exposure will follow well-established experimental procedures. Sessions will begin with a 3-minute relaxation period. Participants will then hold and smell a glass of water for 3 minutes to control for the effects of simple exposure to any potable liquid. Next, participants will hold and smell a glass of their preferred alcoholic beverage for 3 minutes. Order is not counterbalanced because of carryover effects that are known to occur. Participants (who are smokers) will be allowed a smoke break immediately prior to and immediately after the CR assessment. After every 3 minute period, participants will rate their urge to drink on the Alcohol Urge Questionnaire.

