## **8.6. Exploratory Analysis: To determine the effect of low dose on reward responsiveness**

Repeated measures ANOVAs in which Group (Heavy drinking versus light drinking) will be a two level between-subjects factor, and Treatment (endotoxin vs. placebo) is a two level between-subjects factor. The outcome measure is reward responsiveness (captured by the Probabilistic Reward Task and Reward Responsiveness Scale). Sickness symptoms and drinking history will also be included as covariates in these analyses.

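### Sections 8.2, 8.3 and 8.6 do not state the occasions analysed, the term tested or the use of the T0 value, although Section 8.1 powers the study on change from T0 to T2

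*Combined protocol and SAP*

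**What the plan says.** Section 8.1 sizes the study by "selecting the repeated measures ANOVA, within-between interactions design", with f = 0.234, alpha .05 and power of at least 0.80, and reaches 76 completers. The contrast powered is "to detect differences from baseline to peak (T2) inflammatory response". The effect size comes from an earlier endotoxin study's F "statistic of 8.13 for increase in negative mood at T2 after endotoxin infusion".

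The analysis sections then specify:

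- **Section 8.2 (Aim 1):** "in the repeated measures ANOVA models, Group (Heavy drinking versus light drinking) will be a two level between-subjects factor", with Treatment and Cue as the other factors. Cue is also labelled between-subjects.
- **Section 8.3 (Aim 2):** repeated measures ANOVAs with Group "and Treatment (endotoxin vs. placebo) is a two level between-subjects factor. The outcome measure is depressed mood (captured by the POMS").
- **Section 8.6 (exploratory):** the same two factors. "The outcome measure is reward responsiveness (captured by the Probabilistic Reward Task and Reward Responsiveness Scale").

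The covariates in all three are sickness symptoms and drinking history. Only Section 8.4, which is exploratory, names Treatment by Time (T0 to T2), for cytokines and hourly craving.

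The T0 data exist. Section 5.4.5 has participants do the "alcohol cue-exposure paradigm at baseline (T0) during the experimental visit and again approximately 2 hours after" the infusion. The schedule in Section 6.1 agrees, although Section 4.1 mentions only the 2-hour session. POMS is taken at T0 to T4 (Section 6.2.35). The Probabilistic Reward Task and the Reward Responsiveness Scale are given at baseline and T2 (Sections 6.2.34 and 6.2.38).

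**The concern.** A primary analysis should be recoverable from the plan by someone who has not seen the data. Here at least four tests are compatible with the text of one or other primary aim:

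- a comparison at T2 alone;
- Treatment x Time over T0 and T2;
- a Treatment main effect over T0 and T2;
- for mood, either of the last two over all five POMS occasions.

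These tests do not measure the same quantity, and their power differs widely. T0 precedes the infusion, so a main effect that includes T0 is diluted by an occasion on which no treatment effect can exist. A T2-only test sets aside a baseline that is likely to be strongly correlated with the outcome. Section 8.1 itself warns that post-peak points may obscure the effect, so the choice of occasions is not a detail. The reader also cannot confirm that the analysis carried out is the one for which 76 was justified.

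**Working it through.** **1. The plan's own figure.** The stated 0.4687 agrees with sqrt(8.13/37) = 0.4688, and f = 0.234 is half of it. For a within-between interaction with k groups, m occasions and correlation rho, take lambda = f² x N x m / (1 - rho), df1 = (k-1)(m-1) and df2 = (N-k)(m-1). Section 8.1 gives none of k, m or rho, so they are assumed here.

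- k = 2, m = 2, rho = 0: N = 74 is needed, and 76 gives 81% power. This is close to the plan's 76.
- k = 4, m = 2: 76 results at rho of about 0.28 to 0.31.
- k = 2, m = 2, rho = 0.5: N = 38 in total, equal to the stated number per drinking group.

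The figure can be approached only under assumed inputs. Given the contrast that Section 8.1 describes, the repeated factor in each case is Time.

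**2. What the candidate tests deliver.** Assumptions: 76 participants split 1:1 (the plan gives no ratio), so n = 38 per arm; SD of 1 on each occasion; a treatment difference D at T2 and none at T0; T0-T2 correlation rho of 0.5 to 0.7; two-sided alpha 0.05; no other covariates. Power is from the noncentral t with 74 df and noncentrality (effect / s) x sqrt(38/2) = (effect / s) x 4.359.

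| Test | Effect | s | s at rho 0.5; 0.7 |
|---|---|---|---|
| T2 only | D | 1 | 1; 1 |
| Treatment x Time (T0, T2) | D | sqrt(2(1 - rho)) | 1.000; 0.775 |
| T2 adjusted for T0 | D | sqrt(1 - rho²) | 0.866; 0.714 |
| Main effect averaged over T0 and T2 | D/2 | sqrt((1 + rho)/2) | 0.866; 0.922 |

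Example, D = 0.65 and rho = 0.5: the noncentrality is 0.65 x 4.359 = 2.83 for T2 only and for Treatment x Time, 2.83/0.866 = 3.27 for T0-adjusted, and (0.325/0.866) x 4.359 = 1.64 for the average.

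Three values of D are shown. The plan's d is 0.4687. If f = 0.234 is taken literally for a 2 x 2 interaction with the effect only at T2, then D = 4 x 0.234 = 0.936. The middle value, 0.65, is an assumption; it is about the difference that T2 alone detects with 80% power.

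| D (SD) | T2 only | Treatment x Time | T2 adjusted for T0 | Averaged T0/T2 |
|---|---|---|---|---|
| 0.47 | 52% | 52-74% | 64-81% | 21-19% |
| 0.65 | 80% | 80-95% | 90-97% | 37-33% |
| 0.94 | 98% | 98 to >99% | >99% | 64-59% |

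Each range runs from rho 0.5 to rho 0.7. Adjustment for T0 lowers residual variance by rho², that is 25% to 49%.

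**3. Mood averaged over all five POMS occasions.** If the effect were fully sustained from T1 to T4 (assumption) with equal correlations, the effect is 0.8D and s = sqrt((1 + 4 rho)/5), or 0.775 and 0.872. For D = 0.65, power is then 82% to 73%. A shorter-lived effect would give less.

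**4. Limits.** The table is for a two-arm comparison of one outcome. It does not compute Treatment x Cue or any Group x Treatment term.

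**The case against.** The strongest reply is that the label already supplies the answer. Sections 8.3 and 8.6 call for repeated measures ANOVAs and list only between-subjects factors, so Time is the only factor that can repeat. Section 8.1 powers change to T2, and the Aim 2 hypothesis in Section 3.1 concerns greater increases in depressed mood. Together these point to Treatment x Time. This largely stands: a reader might infer that the Aim 2 model excludes Time and that the stated power therefore cannot apply to it, but the text does not support that. What remains open is which occasions enter and which term is tested.

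The reply does not carry over to Aim 1. Every participant receives both cues, so Cue alone can be the repeated factor. A T2-only Group x Treatment x Cue test would be coherent, with water as the within-session control.

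Three other strong readings should also be resisted:

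- A T2-only comparison is not biased by chance baseline differences. Under randomisation it is unbiased with valid type I error, and what it loses is precision.
- The effect is not halved in every averaged analysis. That holds for T0 with T2 alone. Over five POMS occasions T0 carries one fifth of the weight.
- Adding Time is not equivalent to adjusting for T0. At rho = 0.5, Treatment x Time has the same power as T2 alone.

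**Conclusion.** The concern holds as a gap in specification. Neither primary aim has an identifiable occasion set, tested term or use of the T0 value, and exploratory Section 8.6 shares the gap. For Aim 2 the intent is probably Treatment x Time but is not written down. For Aim 1 the pre-infusion cue session may play no part in the analysis.

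The consequence depends on which test is run. Relative to T2 alone, adjusting for T0 raises power from 52% to 64-81% at 0.47 SD and from 80% to 90-97% at 0.65 SD; at 0.94 SD little is left to gain. A main effect averaged over T0 and T2 costs power at every effect size examined. These figures rest on the assumed effect sizes, 1:1 allocation and correlation of 0.5 to 0.7. The ordering of the tests over that correlation range does not depend on the effect size, except that Treatment x Time ties with T2 alone at 0.5.

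**What to change.** Before analysis, state for each of Sections 8.2, 8.3 and 8.6 that the primary analysis is the T2 outcome adjusted for the participant's own T0 value, and name the term tested.

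- **Aim 1:** make Cue a within-subject factor, adjust T2 AUQ for the T0 AUQ under each cue, and name Treatment x Cue and Group x Treatment x Cue as the tests. Entering both T0 scores as participant-level covariates in the repeated PROC GLM model does this; the Cue terms are then tests on the alcohol-minus-water difference at T2, adjusted for both T0 scores.
- **Aim 2:** T2 POMS depressed mood adjusted for T0, with Treatment as the test. Keep T1, T3 and T4 as secondary.
- **Section 8.6:** the same form for each reward measure, still exploratory.

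Treatment x Time restricted to T0 and T2 is a valid alternative that matches Section 8.1 more literally. If the sponsor prefers it, the plan should say so and accept the lower efficiency. Section 8.1 should also state the number of groups, occasions and correlation used, so that 76 can be tied to the chosen test. Section 4.1 should mention the T0 cue session.

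The cost is SAP wording. No visit, measurement or participant is added.

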#### 3.2. Exploratory Aims

Exploratory Aim #1: To test associations between plasma levels of proinflammatory cytokines (IL-6 and TNF-  $\alpha$ ), depressed mood, and alcohol craving during the challenge.

Exploratory Aim #2: To examine sex differences in responses to the endotoxin challenge.

Exploratory Aim #3: To determine the effect of low dose endotoxin (0.8 ng/kg of body weight) on neural alcohol cue-reactivity.

Exploratory Aim #4: To determine the effect of low dose endotoxin (0.8 ng/kg of body weight) on reward responsiveness.

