### 4. STUDY DESIGN

#### 4.1. Design Overview

The study design consists of a randomized, double-blind, placebo-controlled trial of low dose endotoxin. The low dose endotoxin challenge induces a transient systemic inflammatory response with normalization of cytokine levels within hours. This “phasic” inflammation is distinct from chronic (“tonic”) levels of inflammation that may be present with AUD. A total of 38 non-treatment seeking heavy drinking men and women and 38 light drinking healthy controls will participate in the study. Recruitment will be monitored to ensure the two groups are matched by gender. Eligible participants will be randomly assigned to receive a single I.V. infusion of either low dose endotoxin (0.8 ng/kg of body weight) or placebo (same volume of 0.9% saline solution) at the UCLA Outpatient Clinical and Translational Research Center (CTRC). All participants will complete an alcohol cue-exposure paradigm 2 hours post infusion, which is the time of expected peak cytokine response (13, 14). Participants will complete the fMRI alcohol cue reactivity paradigm 3 hours post infusion. Plasma levels of proinflammatory cytokines [i.e.,

Interleukin-6 (IL-6) and tumor necrosis factor- $\alpha$  (TNF-  $\alpha$ ), mood, reward reactivity, and alcohol craving, will be assessed at baseline and then hourly for four hours post infusion.

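### Exploratory Aim 1 asks for associations among cytokines, mood and craving, but section 8.4 specifies only Treatment-by-Time ANOVAs, which do not estimate them

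*Combined protocol and SAP*

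**What the plan says.** Section 3.2 states the aim as "To test associations between plasma levels of proinflammatory cytokines", and names IL-6 and TNF-alpha. The other variables in the association are given there as "depressed mood, and alcohol craving during the challenge". The heading of 8.4 repeats the aim and adds the sex differences of Exploratory Aim 2.

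The method under that heading opens: "Repeated measures ANOVAs will be used to capture the effects of Treatment (endotoxin vs. placebo) by Time (T0 to T2". The rest of the sentence lists cytokines and hourly craving, each as an outcome in its own right, and adds versions of the models with sex as a factor. On covariates, 8.4 says that "sickness symptoms and drinking history will be entered in these models as covariates". It gives no time point for the sickness score.

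Depressed mood is not among the outcomes that 8.4 names. It is analysed in 8.3, as a POMS outcome with Group and Treatment as factors and no cytokine term. Sections 8.2, 8.5 and 8.6 contain no cytokine term either.

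The data for an association analysis are planned. According to 4.1, cytokines, mood and craving "will be assessed at baseline and then hourly for four hours post infusion".

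**The concern.** An ANOVA of cytokines on Treatment and Time shows whether endotoxin raises cytokines. A second ANOVA, of craving on Treatment and Time, shows whether endotoxin changes craving. Neither asks whether the people with the larger cytokine response are the people with more craving or lower mood, which is what the aim asks. The method and the aim do not match, and no other section fills the gap.

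What is at stake is the person-level association. If 8.4 is followed as written, the trial reports none. If an analyst improvises at the end, the choice of model is made after the data are seen. One easy choice, a correlation over both arms without Treatment in the model, would mix the association with the treatment effect.

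**Working it through.** The documents give no sample size, power or alpha for this aim, so there is no plan figure to reproduce. The check has three parts.

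**1. Aim against model terms.**

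| Section | Outcome | Predictors and covariates | Links cytokine to mood or craving? |
|---|---|---|---|
| 8.2 | cue-induced craving | Group, Treatment, Cue; sickness, drinking history | no |
| 8.3 | POMS depressed mood | Group, Treatment; sickness, drinking history | no |
| 8.4 | cytokines; hourly craving (separately) | Treatment, Time, and sex in some models; sickness, drinking history | no |
| 8.5 | neural cue-reactivity | Group, Treatment; sickness | no |
| 8.6 | reward responsiveness | Group, Treatment; sickness, drinking history | no |

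The sex part of 8.4 does have a matching model. The association part has none.

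**2. Does the Treatment-by-Time test carry indirect information on the association?** This was simulated with T0-to-T2 change scores, 38 per treatment arm, 2,000 runs, two-sided alpha 0.05 and no covariates. The following are assumptions, not document figures: cytokine effect 2 SD, craving effect 0.66 SD or 0, within-arm correlation 0 or 0.4. Share of runs that rejected:

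| Craving effect | Within-arm r | Treatment x Time, cytokine | Treatment x Time, craving | Craving on cytokine, adjusted for Treatment |
|---|---|---|---|---|
| 0.66 SD | 0 | 100% | 81.5% | 5.4% |
| 0.66 SD | 0.4 | 100% | 79.1% | 95.7% |
| 0 | 0 | 100% | 4.9% | 4.5% |
| 0 | 0.4 | 100% | 5.0% | 94.8% |

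The within-arm variance of craving is 1 in every row, so the true power of the craving ANOVA is the same at either correlation. The gap between 81.5% and 79.1% is simulation noise: the standard error of each is about sqrt(0.8 x 0.2 / 2000) = 0.009. Only the treatment-adjusted regression separates association from none.

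**3. Scale of the two side issues.**

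*Pooled correlation without Treatment.* Take equal arms, within-arm SD 1, zero within-arm association, a cytokine shift of a SD and a mood shift of b SD. Then

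r = (a/2)(b/2) / sqrt[(1 + a²/4)(1 + b²/4)].

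The shifts are assumptions. The upper value b = 0.94 equals 2 x sqrt(8.13/37), from the F of 8.13 and N of 39 in 8.1. The lower value b = 0.65 has no source in the documents. With N = 76:

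| a | r at b = 0.65 | r at b = 0.94 |
|---|---|---|
| 1 | 0.14 | 0.19 |
| 2 | 0.22 | 0.30 |
| 3 | 0.26 | 0.35 |

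Worked case, a = 3 and b = 0.65: 0.4875 / sqrt(3.25 x 1.1056) = 0.257, p = 0.025. With the same b and a = 2, p is about 0.06. At a = 1, neither value is significant. If b is instead the 0.4687 printed in 8.1, a = 3 gives r = 0.19, p about 0.10.

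*Detectable association.* By Fisher z, with two-sided alpha 0.05, 80% power, no covariates and no multiplicity adjustment, r = tanh[(1.96 + 0.842)/sqrt(n - 3)].

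- n = 38: tanh(2.802/5.916) = 0.44
- n = 76: tanh(2.802/8.544) = 0.32
- n = 19 (one Group-by-Treatment cell, if all cells are equal): tanh(2.802/4) = 0.60

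**The case against.** The strongest reply is that little depends on this. The aim is exploratory, has no stated hypothesis and was not powered, and the data will be there whatever 8.4 says. That stands as a limit on importance. It does not close the gap, because the model that is named cannot answer the question it is named for.

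A reader might go further in four ways that the documents do not support.

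- *That the trial's central premise goes untested.* Section 2.2 frames the premise as a randomised contrast: more cue-induced craving in heavy drinkers after endotoxin than after placebo. Primary Aim 1 addresses that. Only the person-level association is missing.
- *That the plan would report a spurious pooled correlation.* No section proposes one. The figures above are a warning about an improvised substitute, and they depend heavily on the assumed shifts.
- *That 8.4 adjusts for post-infusion sickness.* It says only sickness symptoms. According to 6.2.31 these are rated at baseline and at T1 to T4, so the concern about adjusting for a consequence of endotoxin applies only if a post-infusion score is used.
- *That the endotoxin arm has 38 people.* The 38s in 4.1 and 8.1 are the drinking groups. Section 5.4.1 describes urn randomization without an allocation ratio, so 38 per arm is an assumption.

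**Conclusion.** The concern holds in a limited form. Exploratory Aim 1 has no matching analysis: 8.4 tests treatment effects on cytokines and on hourly craving, 8.3 tests them on mood, and nothing relates one variable to another. Following the plan gives no estimate of the association. This conclusion rests on the text alone and not on the simulated or assumed effect sizes. The primary aims and the sex models are unaffected.

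On size, with equal arms of 38 a within-arm correlation of about 0.44 is detectable with 80% power. About 0.32 would be detectable if all 76 contribute to one common within-arm slope. If cytokines vary little under placebo, the information comes mainly from the endotoxin arm and 0.44 is the more realistic guide. Any slope found would be a non-randomised association, not evidence of mechanism on its own.

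**What to change.** Add an association analysis for this aim to 8.4:

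- Outcomes: T2 AUQ craving and T2 POMS depression. State which T2 AUQ rating is meant, since 6.2.4 has both hourly ratings and ratings within the cue paradigm.
- Predictor: log IL-6 or log TNF-alpha at T2, one cytokine per model. Do not use a 0-4 h area under the curve for a T2 outcome, because it includes T3 and T4 values taken afterwards.
- Adjustment: T0 value of the outcome, T0 log cytokine, Treatment and drinking Group. Include no post-infusion sickness score.
- Reporting: slopes with 95% CIs, labelled exploratory and non-causal. State how multiplicity is handled across the slopes (two cytokines by two outcomes gives four). State the detectable correlation with its assumption about arm sizes.
- Exclude a correlation pooled over arms without Treatment.

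Keep the Treatment-by-Time ANOVAs as the manipulation check and for the sex models.

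The cost is SAP wording and a few extra exploratory regressions and tests. No new data are needed. Section 5.4.4 keeps plasma frozen until the study is complete, so if the assays are still outstanding the model can be fixed before any cytokine value is known.
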